### Target population

The experimental population includes an estimated 60,045 households among consumers who have been discontinued from Medi-Cal, California's Medicaid program, and found eligible for subsidized marketplace coverage.

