### **Likely Effect Size:**

Based on prior phone outreach campaigns carried out by Covered California, we would expect to observe an ITT effect between 0 and 4 percentage points.

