### ***Data and Data Structure***

#### **Outcomes:**

We use Covered California administrative data to examine health insurance take-up behavior and health care utilization among households included in the study.

The primary outcome of interest will be a binary indicator for whether a consumer is effectuated into Covered California plan, either the plan assigned through the auto-enrollment process, or into another plan chosen by the consumer by the end of the month at which outreach was conducted.

Our secondary outcomes will be measured 1-2 years after the intervention when data becomes available will include:

1. Tenure with Covered California (measured in months);
2. A binary indicator for whether someone had an office visit during 1-2 years since the intervention;
3. A binary indicator for whether someone had a prescription drug fill during 1-2 years since the intervention;
4. A binary indicator for whether someone had an emergency room visit during 1-2 years since the intervention;
5. A binary indicator for whether someone had a hospital admission 1-2 years before and 1-2 years after the intervention.
6. Total out-of-pocket spending for the 1-2 years since the intervention
7. A binary indicator for whether someone self-reported being uninsured while filing their taxes;

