#### **Data:**

We will use Covered California administrative data to obtain enrollment outcomes and baseline demographics for our sample and health care claims database to obtain health care utilization and financial outcomes.

We will use data from the Department of Health Care Access and Information for hospital admissions data for all individuals in the intervention. We will use data from the California Franchise Tax Board to measure which individuals reported not having Minimum Essential Coverage (MEC) while filing their state taxes.

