### **Statistical Models**

**Intention-to-treat estimation:** To estimate treatment effects, our primary analysis will be an intent-to-treat (ITT) specification, examining the effect of treatment assignment. We will estimate the effect of the treatment using ordinary least squares (OLS) regression. That is, we will regress the outcome of interest (e.g., take-up) for household  $i$  on the treatment indicator:

$$\text{outcome}_i = \alpha + \beta_1 \text{Treatment}_i + \varepsilon_i$$

The coefficient  $\beta_1$  will be the intent-to-treat estimate of the causal effect of the outreach.

**Complier average causal effect estimation:** We will examine the effects of health insurance (among households induced to enroll in a Covered California as a result of random assignment) on our four utilization outcomes. We anticipate a significant share of noncompliers among those households assigned to receive outreach (intervention) as they may have opted out of assigned plan or not enroll into another Covered California plan. Thus, to augment our analysis of insurance take-up, we will also estimate treatment effects based on treatment receipt (enrollment into Covered California Plan), using two-stage least squares regression (2SLS).

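### The 2SLS is labelled an effect of health insurance, but it estimates the effect of Covered California enrollment against an unstated alternative

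*Combined protocol and SAP*

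**What the plan says.** All references are to the combined protocol and SAP.

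- **Stated target** (Statistical Models, complier paragraph): "We will examine the effects of health insurance (among households induced to enroll in a Covered California as a result of random assignment"), for the four utilization outcomes.
- **Variable instrumented** (same paragraph): effects are based on "treatment receipt (enrollment into Covered California Plan), using two-stage least squares regression (2SLS").
- **Noncompliers** (same paragraph): households for which "they may have opted out of assigned plan or not enroll into another Covered California plan". Coverage from any other source is not mentioned.
- **Population** (Target population): "consumers who have been discontinued from Medi-Cal, California's Medicaid program, and found eligible for subsidized marketplace coverage".
- **Being uninsured** is measured separately. Secondary outcome 7 (Outcomes) is "A binary indicator for whether someone self-reported being uninsured while filing their taxes", and its source (Data) is given as "We will use data from the California Franchise Tax Board to measure which individuals reported not having Minimum Essential Coverage (MEC"). It is not among the outcomes named for the 2SLS.
- **Expected effect on take-up** (Likely Effect Size): "we would expect to observe an ITT effect between 0 and 4 percentage points".

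**The concern.** The label and the instrumented variable are different things. Being enrolled through Covered California is one way of being insured; not being enrolled there is not, by definition, being uninsured. Reading the coefficient as the effect of insurance needs an assumption about what compliers would have had without the outreach. The plan does not make that assumption, and it does not describe the alternative at all.

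This matters for interpretation. If the label is kept, a small or null coefficient could be reported as insurance making little difference to utilization. The same coefficient would also be consistent with outreach having moved some households between sources of coverage. Better outcome data would not help: hospital admissions are to be obtained for all individuals in the study, and the comparison state would still be undefined. The plan also repeats the complier analysis in every subgroup. If the alternative differed between subgroups, their coefficients could differ even where insurance has the same effect.

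**Working it through.** **1. The plan's own figure.** The documents give no figure for the 2SLS. The nearest is the detectable effect on effectuation, which supplies a first-stage size for step 4. Inputs: baseline 6%, 80% power and 0.6 points (Power); two-sided 0.05 (Inference Criteria); 30,101 control and 29,944 treatment (Table 1 totals).

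MDE = (1.960 + 0.842) × √[p̄(1 − p̄)(1/30,101 + 1/29,944)], with p̄ ≈ 0.0628, gives 2.802 × 0.00198 = 0.00555. That is 0.555 points, which rounds to the stated 0.6. Power at exactly 0.6 points is 85.7%. The Table 1 rows sum to 34,935 and 25,610 instead of the printed totals; with those, the MDE is 0.558 points, so nothing here depends on which is used.

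**2. What the 2SLS estimates.** Let u be the share of compliers who would otherwise be uninsured. Let A be the average effect of Covered California enrollment in those compliers, and B the average effect in compliers who would otherwise hold other coverage. Under the standard instrument assumptions:

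2SLS = u·A + (1 − u)·B, so 2SLS − A = (1 − u)(B − A).

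The gap is zero only if u = 1 or B = A (other coverage no different from none). Its sign is the sign of B − A. The documents give none of u, A or B.

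**3. Illustration, on assumed values.** Take A = 20 points, B = 0, and a 4-point first stage on Covered California enrollment (the top of the plan's expected range).

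| u (assumed) | First stage on any insurance = 4u | 2SLS = 20u |
|---|---|---|
| 1.00 | 4 points | 20 points |
| 0.75 | 3 points | 15 points |
| 0.50 | 2 points | 10 points |
| 0.25 | 1 point | 5 points |

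The last column does not change with a first stage of 0.6 or 2 points. It is simply u multiplied by the assumed effect. The direction rests on B = 0: with u = 0.5, A = 20 and B = 30, the 2SLS would be 0.5 × 20 + 0.5 × 30 = 25, above A.

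**4. What outcome 7 could add.** A 2SLS of outcome 7 on Covered California enrollment estimates r − u, where r is the uninsured rate at tax filing among compliers who did enroll. Minus the coefficient is u − r, not u. With assumed u = 0.8 and r = 0.2 it would be 0.6. There is reason to expect r above zero: effectuation is fixed by the end of the outreach month, tenure is a separate outcome, and a household can lapse or have a gap within the tax year.

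Precision, assuming 20% uninsured, everyone filing, a simple two-arm comparison and the Table 1 totals:

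ITT standard error = √[0.2 × 0.8 × (1/30,101 + 1/29,944)] = 0.00326, or 0.33 points.

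Divide by the first stage, treated as known, and multiply by 1.96:

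| First stage | Standard error | 95% half-width |
|---|---|---|
| 0.6 points | 0.54 | 1.07 |
| 2 points | 0.16 | 0.32 |
| 4 points | 0.08 | 0.16 |

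At 30% uninsured the half-widths are about 1.22, 0.37 and 0.18. At the effect the trial was powered for, the interval is wider than the whole range from 0 to 1. At 4 points it is informative.

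**The case against.** The strongest reply is that the paragraph discloses what is estimated. It restricts the effect to households induced to enroll in Covered California and defines receipt as that enrollment, so the estimator is coherent for that narrower effect. This stands, and it is why relabelling is enough.

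A reader might go further and infer that the 2SLS fails to estimate the stated effect, or understates it by some percentage. The documents do not support either. They never say that any complier would otherwise hold other coverage. A separate uninsured outcome implies only that not enrolling and being uninsured are distinct, and mixed eligibility household status is listed as a subgroup without definition. Nor can the case be argued from households that decline the plan. With 6% baseline take-up and at most 4 points added, at least 100 − (6 + 4) = 90% of the treatment arm would not enroll. Under the instrument assumptions those households do not enter the contrast; only compliers do, and nothing is reported about them.

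It is also fair to say that outcome 7 appears to fall under the general ITT model already, so whether outreach lowers the number uninsured will be examined directly. That answers the worry about effectuation as a measure of coverage. It does not answer the label on the 2SLS, which outcome 7 is not linked to.

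**Conclusion.** The point holds as one of labelling and an unstated assumption. The 2SLS identifies the complier effect of Covered California enrollment against an unspecified alternative, and it need not equal the effect of insurance versus no insurance. Reading it that way requires that compliers would otherwise be uninsured (or that any other coverage is equivalent to none), and the plan neither states nor checks this. The size and sign of any gap are unknown; the figures in the illustration rest wholly on assumed u, A and B, and at u = 1 there is no gap. The primary outcome, sample size and ITT estimates are untouched. Minor to moderate, confined to a secondary analysis and its subgroup repeats.

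**What to change.** - In Statistical Models, rename the estimand *effect of Covered California enrollment versus the household's alternative*, and carry that name into the subgroup analyses. Do not report it as the effect of health insurance unless the assumption that compliers would otherwise be uninsured is stated beside it.
- Add secondary outcome 7 to the 2SLS outcomes. Report it as the complier effect on being uninsured at tax filing, with its ITT estimate, its confidence interval and the share filing in each arm.
- Do not present minus that coefficient as the share of compliers who would otherwise be uninsured. Say that lapses or gaps in the tax year pull it below that share.

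Cost: a wording change and one further 2SLS on data already planned, with no change to design or sample. Downsides: the added result covers tax filers only, relies on self-report, and will say little if the first stage is near 0.6 points. The renaming does not depend on it.

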### Power:

To arrive at an estimate for the minimum detectable effect (MDE) for our primary outcome, we assume a baseline health insurance take up of 6 percent. The baseline rate was determined with the historical data on the plan effectuation of individuals disenrolled from Medi-Cal in 2018-

2022 years. The intervention was powered at the 80% level to detect a 0.6 percentage point increase in effectuation rate.

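### Two-stage least squares complier effects are judged at p ≤ 0.05 with no rule tied to first-stage strength, which at the 0.6-point powered effect is borderline overall and weak in subgroups

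*Combined protocol and SAP*

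**What the plan says.** Statistical Models makes ITT the primary analysis: "we will regress the outcome of interest (e.g., take-up) for household" on assignment by ordinary least squares. A complier analysis of four utilization outcomes is then added, "using two-stage least squares regression (2SLS", with the treatment defined as "treatment receipt (enrollment into Covered California Plan". Pre-Specified Subgroup Analyses repeats the complier analysis in every listed subgroup and gives no subgroup sizes. The inference section sets a single criterion, two-tailed p ≤ 0.05 without multiplicity correction. None of these sections mentions a first-stage F, a weak-instrument diagnostic or weak-instrument-robust inference.

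On the likely strength of the first stage, Power states: "The intervention was powered at the 80% level to detect a 0.6 percentage point increase in effectuation rate", from a 6% baseline. Likely Effect Size adds: "we would expect to observe an ITT effect between 0 and 4 percentage points".

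**The concern.** In two-stage least squares (2SLS), assignment is the instrument and enrollment the endogenous treatment, so the first stage is the effect of outreach on enrollment. When that effect is small relative to its standard error, the 2SLS estimate is a ratio with a noisy denominator. Its usual p-value and interval no longer have their nominal error rates, and the usual interval stays finite even where the data do not bound the complier effect.

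At stake is how complier effects, especially in subgroups, are read. A result could be called significant or non-significant by a test whose true error rate is well away from 5%, in either direction, with nothing in the plan to alert the reader.

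**Working it through.** **Inputs.** Baseline 6% and effect 0.6 points (Power); 0 to 4 points (Likely Effect Size); two-sided 0.05 (inference section); arm sizes from Table 1. The Table 1 rows sum to 34,935 control and 25,610 treatment, against printed totals of 30,101 and 29,944. The row sums are used below; the printed totals give nearly the same answers. Subgroup shares, and an equal effect in each subgroup, are assumptions.

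**The plan's own figure.** With the printed totals, a two-sided 5% chi-squared test has 80% power at 0.555 points, which rounds to the stated 0.6. At exactly 0.600 points power is 85.7%. The stated figure reproduces.

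**First-stage strength.** Noncentrality λ = (d/SE)², with SE² = p0(1−p0)/nC + p1(1−p1)/nT; expected F is about λ + 1. At d = 0.006:

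SE² = 0.06×0.94/34,935 + 0.066×0.934/25,610, so SE = 0.002005 and λ = (0.006/0.002005)² = 8.95. Expected F is about 10, with a 57% chance of falling below the conventional 10. The printed totals give λ = 9.15 and 55%.

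λ scales with the subgroup share: half 8.95×0.5 = 4.5, third 3.0, fifth 1.8, tenth 0.9.

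At larger effects the overall λ is about 24 at 1 point, 89 to 93 at 2 points and 312 to 335 at 4 points. The lower figure uses each arm's own variance, the upper a single residual variance pooled over arms. For λ = 10 the effect must be about 0.63 points overall, 1.44 to 1.47 in a fifth and 2.08 to 2.13 in a tenth. A tenth at 2 points has λ = 89×0.1 = 8.9, about as weak as the whole sample at 0.6 points.

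**Size of the nominal 5% test.** Draw the first-stage statistic as N(√λ, 1) and the reduced-form statistic as N(0, 1) under zero effect, with correlation ρ. With b their ratio, reject when (reduced form)²/(1 − 2bρ + b²) exceeds 3.84 (400,000 draws per cell):

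| Sample at 0.6 points | λ used | ρ = 0 | 0.3 | 0.5 | 0.8 | 0.95 |
|---|---|---|---|---|---|---|
| All | 9.1 | 1.2% | 2.5% | 4.3% | 7.2% | 8.4% |
| Half | 4.6 | 0.5% | 1.7% | 4.0% | 8.5% | 10.2% |
| Third | 3.0 | 0.3% | 1.3% | 3.5% | 9.4% | 11.7% |
| Fifth | 1.8 | 0.1% | 0.9% | 2.9% | 10.4% | 13.9% |

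Size crosses 5% at ρ of about 0.57 overall and 0.61 in a fifth. At λ = 24 (1 point overall) the range over the same ρ is 3.1% to 6.5%.

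**Which side of 0.6 applies.** This depends partly on whether use is recorded for people who do not enroll. The Data section promises a source "for hospital admissions data for all individuals in the intervention", but for other use cites only a "health care claims database to obtain health care utilization and financial outcomes", without saying whether it covers non-enrollees. Two illustrations with 6% enrolled:

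- Use seen for everyone, at 5% in non-enrollees and up to ten times that (50%) in those who enroll regardless. The correlation is at most 0.06×0.94×0.45/√(0.0564×0.0711) = 0.40, where 0.0711 = 0.077×0.923 is the outcome variance. The test is conservative.
- Use seen only for enrollees, 50% or 80% of whom use care. A zero complier effect then means compliers have no recorded use. The correlation is 0.0564×0.5/√(0.0564×0.0291) = 0.70, or 0.0564×0.8/√(0.0564×0.0457) = 0.89. The test is anti-conservative.

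**The case against.** The strongest reply is that the plan already protects itself. ITT is primary and 2SLS is there to augment it. A reader might infer that the plan leaves open which of two p-values counts for a utilization outcome. It does not: Statistical Models ranks ITT above 2SLS. A reader might also infer that the first stage would go unexamined, but the take-up ITT, overall and by subgroup, is in substance that first stage. What stands is narrower: the 2SLS result is still judged at p ≤ 0.05 whatever the first stage shows.

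Second, 0.6 points is a detection limit, not a forecast, and at 2 points, the middle of the plan's range, the overall instrument is strong. This is right, and it rules out the reading that the complier analysis is bound to fail. But the range begins at 0, and an analysis should hold up at the effect it was powered for.

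Third, a reader might infer an excess of false positives. The documents do not support that: below a correlation of about 0.6 there are too few. The 14% figure needs a fifth-size subgroup, a 0.6-point effect and a correlation of 0.95 together, and neither illustration above reaches 0.95. The fair statement is that calibration is unknown.

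Fourth, the Anderson-Rubin test of zero effect is the ITT test already planned. This is true; the gain lies in the confidence set, the reported F and a criterion that does not depend on first-stage strength.

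**Conclusion.** The point holds as a gap in a secondary analysis, not as an error in the primary one. At the powered effect the first stage is borderline overall (noncentrality about 9) and weak in subgroups (about 4.5, 3.0 and 1.8 in a half, third and fifth). The nominal 5% test then has a true size of about 1.2% to 8.4% overall and 0.1% to 14% in a fifth. The overall problem largely disappears at larger effects within the plan's range.

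This rests on assumed subgroup shares, an equal effect in each subgroup, and an error correlation that the documents do not give. It also assumes that the 2SLS first stage matches the primary outcome. The latter counts effectuation "by the end of the month at which outreach was conducted", whereas the 2SLS enrollment variable has no stated window, so the actual first stage could be stronger or weaker.

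**What to change.** Add to Statistical Models and Pre-Specified Subgroup Analyses:

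> For each complier effect, overall and by subgroup, we will report the first-stage F from the same model and sample, and the Anderson-Rubin 95% confidence set alongside the 2SLS estimate. Significance will be based on the Anderson-Rubin test, which for zero effect is the ITT test of that outcome. Where the set is unbounded, we will state that the data do not bound the complier effect.

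Also state the time window of the enrollment variable, so that readers can tell whether the take-up ITT is its first stage.

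The cost is a few sentences and a standard post-estimation step, with no new data. With a strong first stage the set nearly equals the 2SLS interval: for a zero estimate and zero correlation its width ratio is 1/√(1 − 3.84/λ), about 1.02 at λ = 89 (2 points).

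The downside is that many sets will be unbounded if the effect is small. This happens when the first-stage |z| is below 1.96, with probability Φ(1.96 − √λ) − Φ(−1.96 − √λ). At 0.6 points this is 15% overall (λ = 8.95) and 73% in a fifth (λ = 1.79). Using the 6% variance in both arms (λ = 9.43 and 1.89) gives 13% and 72%. The change repairs only the weak-instrument problem: the Anderson-Rubin test is no better calibrated than the ITT test in the same model.

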### **Pre-Specified Subgroup Analyses**

We will examine treatment heterogeneity by race and ethnicity of the head of household, written or spoken language, gender of head of household, income group measured by the percentage of the federal poverty level, net premium of assigned plan, age bracket (30 years and younger, 31-49 years old, older than 50 years old), health status as measured by HCIAI discharge data, mixed eligibility household status. Same subgroup analyses will be performed for our complier average causal effect analysis.

### **Inference Criteria, Including Any Adjustments for Multiple Comparisons:**

We will not perform any corrections for multiple hypothesis testing, and we will use two-tailed tests with p-values  $\leq 0.05$  to denote statistically significant effects.

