## Design Document and Analysis Plan

### Project Objective

In May 2023, Covered California, California's ACA marketplace, implemented its automatic enrollment program for individuals losing Medicaid coverage, as defined by Senate Bill 260. If individuals are found eligible for subsidized marketplace coverage, individuals will be automatically enrolled in the lowest cost silver plan available to them, but individuals must still take action to confirm their plan or pay their first month's premium. To identify whether the phone outreach is the effective outreach strategy to increase take-up in this population, Covered California implemented this intervention. The results of this evaluation will inform operational and budgeting decisions.

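### One uncorrected p ≤ 0.05 rule labels every secondary, complier and subgroup result as significant, over a family of tests the plan does not define

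*Combined protocol and SAP*

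**What the plan says.** The Inference Criteria section has one rule. It says "We will not perform any corrections for multiple hypothesis testing", then "we will use two-tailed tests with p-values" at or below 0.05 "to denote statistically significant effects". The rule is not limited to any outcome or analysis.

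The analyses it covers are listed in three other sections:

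- **Outcomes.** There is one primary: "The primary outcome of interest will be a binary indicator for whether a consumer is effectuated into Covered California plan". Seven numbered secondary outcomes follow, introduced by "Our secondary outcomes will be measured 1-2 years after the intervention when data becomes available will include".
- **Statistical Models.** ITT by ordinary least squares is the primary analysis. A complier analysis by 2SLS is added "on our four utilization outcomes", with assignment as the instrument for plan enrollment.
- **Pre-Specified Subgroup Analyses.** Eight factors are named: race and ethnicity, language, gender, income, net premium, age bracket, health status and mixed-eligibility status. Then: "Same subgroup analyses will be performed for our complier average causal effect analysis".

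Levels are given only for age (three brackets). The plan does not say which outcomes are examined by subgroup, or whether heterogeneity is judged by an interaction test or by separate tests within levels. No section calls any of these results exploratory or sets a different standard for them.

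**The concern.** A 5% threshold limits false claims for one test. Used over a long and open-ended list, with the same label each time, it can be expected to produce some labelled effects by chance. The plan does not separate those from the one result it was powered to deliver.

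The label matters because of the stated use: "The results of this evaluation will inform operational and budgeting decisions". Language, net premium and income are natural grounds for deciding which households to telephone. A chance subgroup result reported as a significant effect could be read as a reason to target or withdraw outreach. Since the family of tests is undefined, a reader who wanted to discount the subgroup results for multiplicity could not tell by how much.

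**Working it through.** **The plan's own figure.** The Power section gives a detectable difference of 0.6 percentage points at 80% power from a 6% baseline. Table 1 prints totals of 30,101 control and 29,944 treatment. For two proportions with pooled null variance and two-sided 0.05:

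- At 0.06 versus 0.066, mean 0.063, the standard error is √[0.063 × 0.937 × (1/30,101 + 1/29,944)] = 0.00198.
- Power = Φ[(0.006 − 1.96 × 0.00198)/0.00198] = Φ(1.07), about 86%.
- Solving for 80% power gives 0.555 points, which rounds to the plan's 0.6.

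The Table 1 rows add up to 34,935 and 25,610 rather than the printed totals. With those sizes the detectable difference is 0.558 points, so nothing here changes. The power statement concerns one test, and that test keeps its 0.05 level.

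**Which tests can be counted at 5% each.** The 2SLS tests cannot. If outreach changes nothing, assignment does not move enrollment either, and the first stage is zero. Let f and r be the first-stage and reduced-form z-statistics, with correlation ρ between the errors. The squared 2SLS t-statistic is then r²/[1 − 2ρ(r/f) + (r/f)²]. With one million simulated draws and a zero first stage, a nominal 5% test rejected in 0.01% of draws at ρ = 0, 1.5% at 0.5, 13% at 0.8 and 40% at 0.95. The complier tests are therefore left out of the count, as is the primary test.

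**Expected false positives among the remaining ITT tests.** The expected number is the number of tests × 0.05, which holds whatever the dependence. Where tests are counted level by level, I assume the fewest possible levels: 7 factors × 2 + 3 for age = 17. The last row assumes 25 levels instead.

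| Reading | Tests | Expected |
|---|---|---|
| Seven secondary outcomes only | 7 | 0.35 |
| + one interaction test per factor, take-up only | 7 + 8 = 15 | 0.75 |
| + 17 levels, take-up only | 7 + 17 = 24 | 1.2 |
| + one interaction test per factor, all eight outcomes | 7 + 8 × 8 = 71 | 3.55 |
| + 17 levels, all eight outcomes | 7 + 17 × 8 = 143 | 7.15 |
| + 25 levels, all eight outcomes | 7 + 25 × 8 = 207 | 10.35 |

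**Chance of at least one.** Under independence this is 1 − 0.95^7 = 30% for the seven secondaries and 1 − 0.95^15 = 54% for the 15-test reading. Under any dependence, the seven secondaries cannot exceed 7 × 0.05 = 35%.

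**The case against.** The case for the plan is a reasonable one. It names a single primary outcome and calls ITT the primary analysis, so a hierarchy exists. The decision not to correct is declared in advance, and the outcomes and factors are listed. A reader can apply a correction to the overall secondary results, for example 0.05/7 = 0.007. The Project Objective ties the decision to whether phone outreach raises take-up, which is the primary test. Leaving secondary outcomes uncorrected behind one primary is a defensible choice.

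Most of this stands. The primary conclusion is not at risk, correction is not obligatory, and an unadjusted p-value from a listed test is weaker evidence rather than none. It does not answer the narrower point. The hierarchy is one of names only: the same threshold and label apply at every tier, and the subgroup family cannot be counted from the text.

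A reader might also infer a firmer number. Counting 12 overall tests (8 ITT, 4 complier), 17 levels on take-up and 17 × 4 complier subgroup tests gives 97 tests and 97 × 0.05 = 4.9. Crossing the levels with all eight ITT outcomes gives 12 + 136 + 68 = 216 and 10.8. The documents do not support a claim of 5 to 11 false effects. It assumes levels and crossings that the plan does not give, and it includes the primary test. It also gives 4 + 68 = 72 2SLS tests a 5% error rate under a null where they do not have one. If the first stage is strong instead, outreach does change take-up, and each 2SLS test largely repeats the ITT test of the same outcome.

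**Conclusion.** The point holds as a defect of labelling and definition. Followed as written, the rule can be expected to call some chance results significant effects. If outreach affects none of the outcomes, the expected number among the non-primary ITT tests is about 0.75 on the narrowest subgroup reading and about 7 on the broad reading with the fewest levels. It is higher still with more levels.

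That range rests on three assumptions: 5% size for each ITT test; the level counts shown; and exclusion of the complier tests, whose error rate could lie well below or well above 5%. The 54% figure also assumes independence, which correlated outcomes would not satisfy exactly.

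The documents do not show that the primary result is compromised, or that a particular budget decision turns on a secondary or subgroup p-value. This is a cheap improvement that limits what the evaluation can claim.

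**What to change.** Amend the Inference Criteria section as follows.

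1. Reserve the term *statistically significant*, at two-sided 0.05, for the single primary ITT test on take-up.
2. Report all secondary, complier and subgroup results as exploratory, with estimates and 95% confidence intervals.
3. Judge heterogeneity by one interaction test per factor. State the levels of each factor and the outcomes to which the subgroup analyses apply.
4. If significance is to be claimed beyond the primary test, first define the family, including any complier and subgroup tests in it, and name the adjustment. Holm across the seven secondary ITT outcomes is one example. A procedure for the secondary outcomes alone would leave the complier and subgroup tests uncovered.

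The cost is a change of wording and, if item 4 is used, a column of adjusted p-values. Secondary and subgroup claims become harder to make. The primary test keeps its level and power. On timing, the first cohort is August 2023, the document was last updated on June 5, 2024, and the secondary outcomes are measured 1–2 years after the intervention. No cohort had reached one year at that update, so the rule could still have been set before those outcomes were complete.
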